### 3.3.2 Overall Survival

The OS is defined as the time from the date of first dose of durvalumab until death due to any cause.

- $OS \text{ (days)} = (\text{date of death or censoring}) - (\text{date of first dose of durvalumab}) + 1$

Any patient not known to have died at the date of DCO will be censored at the last recorded date at which the patient was known to have been alive, or at date of DCO, if known afterwards.

The date that an individual patient was last known to be alive will be identified exclusively using the data recorded within the SURVIVE and DEATH modules of the electronic case report form (eCRF).

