HIV: Human immunodeficiency virus; IP: Investigational product; LFT: Liver function test; max.: maximum; MRI: Magnetic resonance imaging; PD: Progression of disease; CCI [REDACTED]

CCI [REDACTED]; q4w, q8w, q12w: Every 4, 8, 12 weeks, respectively; q28d: Every 28 days; QoL: Quality of life; RECIST 1.1: Response Evaluation Criteria in Solid Tumours version 1.1; SAE: Serious adverse event;

sCRT: Sequential chemoradiation therapy; T3: Triiodothyronine; T4: Thyroxine; CCI [REDACTED]; TSH: Thyroid-stimulating hormone; CCI [REDACTED]
CCI [REDACTED]

Table 2 Schedule of assessments for patients who have discontinued study drug

| Evaluation | Time since last dose of IP | | | | | | For details, see Section |
|--|--|-------------------------|---|---|---|---|--------------------------|
| | Day (±3) | Months (±1 week) | | | | 12 months and every 3 months (±2 weeks) | |
| | 30 | 2 | 3 | 6 | 9 | | |
| Physical examination (full) | X | | | | | | 8.2.2 |
| Vital signs (temperature, respiratory rate, blood pressure, and pulse) | X | | | | | | 8.2.3 |
| Body weight | X | X | X | | | | 8.2.3 |
| Pregnancy test ^a | X | As clinically indicated | | | | | 8.2.1 |
| AE/SAE assessment | X | X | X | | | | 8.3 |
| Concomitant medications | X | X | X | | | | 6.4 |
| CCI | CCI | | | | | | 8.2.6 |
| Subsequent anticancer therapy ^{c,d} | ← → | | | | | | |
| Survival status ^e | | X | X | X | X | X | 8.1.1 |
| Haematology | X | X | X | | | | 8.2.1 |
| Clinical chemistry | X | X | X | | | | 8.2.1 |
| Urinalysis | As clinically indicated | | | | | | 8.2.1 |
| TSH (reflex free T3 or free T4) ^f | X | X | X | | | | 8.2.1 |
| CCI | X | X | X | | | | 8.1.2.1, 8.1.2.2 |
| CCI | X | X | X | | | | 8.1.2.3 |
| Tumour assessment as per local institutional standard care (CT or MRI) (RECIST 1.1) ^h | Additional scans to be completed per standard practice post progression (not mandatory to be recorded in eCRF). Patients who permanently discontinue IP for reasons other than objective RECIST 1.1 disease progression should continue to have RECIST 1.1 assessments performed q8w ±1 week beginning 8 weeks after IP treatment initiation for the first 52 weeks and q12w ±1 week thereafter until clinical progression/deterioration or RECIST 1.1-defined radiological progression plus 1 or more additional follow-up scans for confirmation of progression until confirmed radiological progression, the end of study, death, study discontinuation, or Sponsor decision (whichever comes first). | | | | | | 8.1 |

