^a For women of childbearing potential only. A urine or serum pregnancy test is acceptable.

- b [REDACTED]
- c Details of any treatment for NSCLC (including surgery) post the last dose of IP must be recorded in the eCRF. At minimum, collect the start date and description of the subsequent anticancer therapy.
- d For patients who discontinue the IP following progression, available readings of CT/MRI from local practice will be collected from patients' medical charts while information on subsequent anticancer treatment is collected.
- e Patients who decline to return to the site for evaluations should be contacted by telephone as an alternative. In addition to the regularly scheduled survival follow-up, patients may be contacted in the week following DCO to confirm survival status. Every effort should be made to contact patients by telephone to follow and record survival status.
- f Free T3 or free T4 will only be measured if TSH is abnormal or if there is clinical suspicion of an AE related to the endocrine system.
- g Will be administered using a site-based electronic device. PRO questionnaires are to be completed prior to any other study procedures and before discussion of disease progression to avoid biasing the patient's responses to the questions.
- h Only for patients yet to progress, RECIST 1.1 assessments will be performed on images from CT (preferred) or MRI, each preferably with IV contrast, of the chest and abdomen (including the entire liver and both adrenal glands). Additional anatomy should be image-based on signs and symptoms of individual patients. For patients who are clinically stable and being treated through radiological progression, the follow-up scan performed after a RECIST 1.1-defined PD should be performed preferably at the next (and no later than the next) scheduled imaging visit, and no less than 4 weeks after the prior assessment of PD; special Confirmation of Radiological Progression Criteria apply for tumour assessments on the follow-up scan (Appendix F). If an unscheduled assessment was performed and the patient has not progressed, every attempt should be made to perform the subsequent assessments at their scheduled visits (relative to the date of IP treatment initiation). The modality of tumour assessment should be the same throughout the study.

AE: Adverse event; CT: Computed tomography; DCO: Data cut-off; eCRF: Electronic case report form; [REDACTED]

[REDACTED]

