8.1.1 Survival assessments

Assessments for survival must be made q12w (± 2 weeks) following treatment discontinuation. Survival information may be obtained via telephone contact with the patient or the patient's family or by contact with the patient's current physician. The details of first and subsequent therapies for cancer, after discontinuation of treatment, will be collected.

In addition, patients on treatment or in survival follow-up will be contacted following the DCO for the primary analysis and all subsequent survival analyses to provide complete survival data. Survival calls will be made following the date of DCO for the analysis (these contacts should generally occur within 7 days of the DCO). If participants are confirmed to be alive or if the death date is after the DCO date, then these participants will be censored at the date of DCO.

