- $PFS \text{ (days)} = \text{Date of event or Censor date} - \text{treatment start date} + 1$
- Patients who have not progressed or died at the time of analysis will be censored at the time of the latest date of assessment from their last evaluable assessment. However, if the patient progresses or dies after 2 or more missed visits, the patient will be censored at the time of the latest evaluable assessment prior to the 2 missed visits. If the patient has no evaluable visits or does not have baseline data, he/she will be censored at Day 1 unless he/she dies within 2 visits of baseline, in which case the date of death is the event date.
- 8 **OS:** Defined as the time from the first date of treatment until death due to any cause.
- $OS \text{ (days)} = \text{Death date or Censor date} - \text{treatment start date} + 1$
- Any patient not known to have died at the time of analysis will be censored based on the last recorded date on which the patient was known to be alive.
- 9 **Lung cancer mortality (NSCLC-related death):** Defined as the time from the date of treatment start until death due to lung cancer.
- $\text{Time to NSCLC-related deaths (days)} = \text{NSCLC-related death date or Censor date} - \text{treatment start date} + 1$
- Any patient not known to have died due to lung cancer will be censored based on the last recorded date on which the patient was known to be alive or died due to reason other than lung cancer.
- 10 **ORR:** Based on Investigator-assessed response to treatment of CR and PR, per RECIST1.1.
- 11 **DoR:** Defined as the time from the date of first documented response per RECIST1.1 until the first date of documented progression per RECIST1.1 or death in the absence of disease progression

DoR (days) = Date of PFS event or censoring – Date of first response +1

The end of response should coincide with the date of progression or death from any cause used for the PFS endpoint. If a patient does not progress following a response, then the patients' DoR will be censored at the PFS censoring time. DoR will not be defined for those patients who do not have a documented response.

12

CCI [REDACTED]

13 **Treatment duration:** Defined as Treatment end date – Treatment start date +1; will be summarized.

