### 1.2.3 Overall Survival Assessments

Patients will be followed for survival status every 12 weeks (q12w) following treatment discontinuation, until death, withdrawal of consent or the end of the study. These contacts may be conducted by phone and the survival data collected will be reported in the clinical database for the final study analysis.

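### The SAP takes last-known-alive dates only from the SURVIVE and DEATH modules, so patients untraceable at data cut-off lose documented survival time or have no defined censoring date

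*SAP*

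**What the plan says.** SAP 3.3.2 censors a patient not known to have died so that the patient is "censored at the last recorded date at which the patient was known to have been alive, or at date of DCO, if known afterwards". It then limits the source: the last-known-alive date "will be identified exclusively using the data recorded within the SURVIVE and DEATH modules" of the eCRF. SAP 3.3.6 repeats the restriction for lung cancer mortality. Neither section says what to do when those modules hold no record.

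Routine survival status starts after treatment. SAP 1.2.3: "Patients will be followed for survival status every 12 weeks (q12w) following treatment discontinuation". Protocol 8.1.1 likewise places the 12-weekly checks "following treatment discontinuation. Survival information may be obtained via telephone contact with the patient" or through family or the current physician. In Protocol Table 2 the "Survival status" row has its first entry at Month 2 after the last dose and none at Day 30. Treatment may last 24 months.

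Two provisions supplement that schedule. Protocol 8.1.1 adds that "patients on treatment or in survival follow-up will be contacted following the DCO for the primary analysis and all subsequent survival analyses", and those confirmed alive are censored at the DCO. Protocol 7.2 requires vital status to be re-checked for all enrolled patients, including those who withdrew or are potentially lost.

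The protocol's own OS rule sets no limit on source. Under 9.4 a patient not known to have died "will be censored based on the last recorded date on which the patient was known to be alive". Under 7.2 a patient who cannot be reached by the end of the study is censored at the latest follow-up contact.

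**The concern.** A patient on treatment generates many dated proofs of being alive: infusions, vital signs, laboratory samples, scans. The SAP bars all of them from the OS censoring date. If such a patient leaves before any SURVIVE entry exists and cannot be traced, months of documented survival drop out, and the programmer has to invent a censoring date. PFS has an explicit Day 1 rule for patients without evaluable data (SAP 3.3.1); OS has no counterpart.

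The loss is one-sided. Deaths can still be recovered, since 7.2 allows public death registries to be searched where lawful. The documents do not say that absence from a registry yields a SURVIVE alive-date. The SAP rule also departs from Protocol 9.4 and 7.2 without appearing among the changes in SAP section 6; the SAP amendment history describes it as a clarification. At stake are OS12, OS24, OS36, median OS and the lung cancer mortality curve, each also reported for the PS 2 cohort of up to 30 patients.

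**Working it through.** **The two rules for the same patient.** Take a patient dosed and scanned up to month 10 who then withdraws from all follow-up, has no SURVIVE entry and cannot be traced at the DCO. Protocol 9.4 and 7.2 censor at about month 10. SAP 3.3.2 gives no date.

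**Direction.** The Kaplan-Meier estimate is S(t) = Π(1 − d_j/n_j). Moving a censoring date earlier leaves each d_j unchanged and can only reduce n_j, so no factor rises. For a given data set the SAP rule therefore cannot raise the curve. For lung cancer mortality, a lower curve means higher estimated mortality.

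**Small example, PS 2 cohort.** With 30 patients, 9 deaths by month 10 and one survivor leaving then, survival is 21/30 = 70.0%. With that survivor censored at Day 1 it is 20/29 = 69.0%.

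**Size.** The plan gives no figure to reproduce, so the two rules were compared by simulation, with 200,000 patients per scenario.
- From the documents: first survival check 2 months after last dose; treatment capped at 24 months; final DCO about 27 months (24 months plus 90 days) and primary DCO 6 months after the last patient's first dose.
- Assumed, not in the documents: exponential OS with median 20, 25 or 35 months; median treatment duration 7 or 12 months; uniform 20-month accrual; a constant monthly hazard of becoming untraceable of 0.003, 0.006 or 0.012; Day 1 censoring under the SAP rule when no SURVIVE record exists.
- A patient counts as untraceable if loss occurs before the first survival check, before death and before the DCO. Under the any-date rule that patient is censored at the time of loss. All others are traced at the DCO.

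Final analysis, SAP rule minus any-date rule, ranges over the six combinations of OS median and treatment duration:

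| Loss hazard per month | Untraceable, no SURVIVE record | OS12 (points) | OS24 (points) | OS36 (points) | Median (months) |
|---|---|---|---|---|---|
| 0.003 | 2.5–3.7% | −0.3 to −0.6 | −0.3 to −0.5 | −0.2 to −0.4 | −0.2 to −0.4 |
| 0.006 | 5.0–7.1% | −0.6 to −1.2 | −0.6 to −1.0 | −0.4 to −0.7 | −0.4 to −0.7 |
| 0.012 | 9.5–13.6% | −1.2 to −2.4 | −1.1 to −2.0 | −0.8 to −1.5 | −0.8 to −1.5 |

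Example: for OS median 25 and treatment median 12 months, true OS24 is 0.5^(24/25) = 0.514. With 6.6% untraceable, the any-date rule gives 0.514 and the SAP rule 0.504, a difference of −1.0 point.

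At the primary analysis the same inputs give 2.2–10.7% untraceable and OS24 differences of −0.2 to −1.4 points.

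**No loss.** If every patient is traced at the DCO, the rules agree at the primary analysis (OS12 0.713 against 0.713 and 0.715 against 0.715 for OS median 25). At the final analysis they agree even without the DCO call (OS36 0.361 against 0.361).

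**Scale.** With n = 150 and OS24 near 0.51, ignoring censoring, the 95% half-width is 1.96 × √(0.51 × 0.49/150) = 0.080, or 8 points.

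**The case against.** The safeguards are strong. The DCO contact in 8.1.1 explicitly includes patients on treatment, and the SAP accepts a DCO censoring date. Stopping the drug does not end participation, and 7.1.1 requires a modified follow-up through relatives, physicians or records. Survival follow-up continues after withdrawal unless that consent is expressly withdrawn (7.3). The re-check in 7.2 updates the applicable eCRF modules. The share untraceable by every route could be very small, and neither that share nor Day 1 censoring is stated in the documents. Naming source modules is partly ordinary SAP detail. All of this stands, and it keeps the point small. It does not supply a censoring date for the remaining patient or remove the conflict with Protocol 9.4 and 7.2.

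A reader might infer that, because no survival form is scheduled during treatment, on-treatment survival is discarded wholesale and the primary analysis is the most exposed. If the DCO contact did not exist, 19% to 36% of patients would lack a SURVIVE or DEATH record at that cut-off under the assumptions above, and OS12 would fall by 5 to 13 points. The documents do not support that reading, because 8.1.1 requires the contact. Footnote e, "patients may be contacted in the week following DCO to confirm survival status", does not rescue it: the footnote belongs to Table 2, for patients who have discontinued study drug, and does not govern patients still on treatment.

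**Conclusion.** The point holds for a narrow group: patients who leave during treatment or before the first post-treatment survival check and cannot be traced at the DCO. For them the SAP discards documented survival or leaves the censoring date undefined, contrary to Protocol 9.4 and 7.2 and without mention in SAP section 6. The undefined date and the conflict depend on no simulation.

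The effect is downward or nil. It is zero if all patients are traced and entered in SURVIVE, and roughly 0.3 to 2 points on OS24 at the final analysis if about 2.5% to 14% are untraceable and censored at Day 1. Both conditions are assumptions. Even the upper end is well inside the sampling error for the whole trial.

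Some of this cannot be checked. Protocol Table 1 is only partly readable, the eCRF specification is not in the documents, and it is inferred, not stated, that DCO contacts with on-treatment patients are entered in SURVIVE. OS and lung cancer mortality are secondary and descriptive, with no hypothesis tested (Protocol 9.1). Priority: minor.

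**What to change.** 1. In SAP 3.3.2 and 3.3.6, define last known alive as the latest date from any eCRF module that proves the patient was alive (dosing, visit, vital signs, laboratory sample, tumour assessment, AE start, SURVIVE), capped at the DCO.
2. State that DCO contacts with on-treatment patients are entered in SURVIVE.
3. Align footnote e of Protocol Table 2, which says patients may be contacted after the DCO, with 8.1.1, which says they will be.

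The cost is a few lines of wording and a standard derivation from data already collected. No new assessments are needed. If the sponsor prefers to keep the module restriction, SAP section 6 should list it as a change from the protocol, and 3.3.2 and 3.3.6 should give a censoring date for patients with no record in either module.

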### 3.3.3 Objective Response Rate

The ORR is defined for the SAF as follows:

- The ORR is the proportion (%) of patients with an overall response of CR or PR (confirmed by a follow-up scan at least 4 weeks after showing CR or PR).

A confirmed response of CR/PR means that a response of CR/PR is recorded at one visit and confirmed by repeat imaging, preferably at the next regularly scheduled imaging visit, and not less than four weeks after the visit when the response was first observed, with no evidence of progression between the initial and CR/PR confirmation visit. Both visits contributing to the confirmed response must be prior to any subsequent anti-cancer therapy for the patient to be considered as a responder.

Data obtained up until progression, or the last evaluable assessment in the absence of progression, will be included in the assessment of the ORR. Responses that occur after the start of subsequent anti-cancer therapy must be excluded from the derivation of ORR (ie, only responses that occur prior to receiving subsequent therapy will be included in the numerator).

### 3.3.4 Best Objective Response

Best objective response (BoR) is the best response a patient has had after Day 1 up until progression, or the last evaluable assessment in the absence of progression. Responses that occur after the start of subsequent anti-cancer therapy must be excluded from the derivation. Categorization of BoR will be based on RECIST using the following response categories: CR, PR, SD, PD and NE.

CR or PR must be confirmed. For determination of a best response of SD, the earliest of the dates contributing towards a particular overall visit assessment will be used. SD should be recorded at least 8 weeks minus 1 week, ie, at least 49 days (to allow for an early assessment within the assessment window), after durvalumab initiation. For CR/PR, the initial overall visit assessment that showed a response will use the latest of the dates contributing towards a particular overall visit assessment.

For patients whose progression event is death, BoR will be calculated based upon all evaluable

RECIST assessments prior to death.

For patients who die with no evaluable RECIST assessments, if the death occurs  $\leq 9$  weeks (ie, 8 weeks + 1 week to allow for a late assessment within the assessment window) after durvalumab initiation, then BoR will be assigned to the progression (PD) category. For patients who die with no evaluable RECIST assessments, if the death occurs  $> 9$  weeks after Day 1 then BoR will be assigned to the NE category.

A patient will be classified as a responder if the RECIST criteria for a CR or PR are satisfied at any time following Day 1, prior to RECIST progression and prior to starting any subsequent cancer therapy.

### 3.3.5 Duration of Response

For patients who are classified as responders (see Section 3.3.3), the DoR is defined as the time from the date of first documented response (which is subsequently confirmed) until the first date of documented progression or death in the absence of disease progression.

- $\text{DoR} = (\text{date of PFS event or censoring}) - (\text{date of start of response}) + 1$

The date of the end of response will coincide with the date of disease progression or death from any cause used for the PFS endpoint (see Section 3.3.1). If a patient does not progress following a response, then their DoR will be censored at the date used in the PFS censoring. The date of the initial response will be defined as the latest of the dates contributing toward the first visit response of CR or PR that was subsequently confirmed. DoR will not be defined for those patients who do not have documented confirmed response.

DoR will also be obtained using the algorithm described above for the RECIST 1.1 site Investigator tumour data.

### 3.3.6 Lung Cancer Mortality

The lung cancer mortality (NSCLC-related death) is assessed using the deaths which are reported as 'NSCLC-related' and is defined as the time (days) from the date of first dose of durvalumab until date of death due to lung cancer as follows:

- $\text{Time to lung cancer mortality} = (\text{date of NSCLC-related death or censoring}) - (\text{date of first dose of durvalumab}) + 1$

Any patient not known to have died at the date of DCO will be censored at the last recorded date at which the patient was known to have been alive, or at date of DCO, if known afterwards.

The date that an individual patient was last known to be alive will be identified exclusively using the data recorded within the SURVIVE and DEATH modules of the electronic case report form (eCRF).

## 3.4 Exploratory Variables

CCI

### 3.4.1

CCI [Redacted]

CCI [Redacted]

[Redacted]

[Redacted]

[Redacted]

[Redacted]

[Redacted]

CCI [Redacted]

[Redacted]

[Redacted]

[Redacted]

CCI [REDACTED]

### 3.4.1.1 CCI [REDACTED]

CCI [REDACTED]

CCI [REDACTED]

[REDACTED]

[REDACTED]

[REDACTED]

[REDACTED]

CCI

[Redacted]

CCI

[Redacted]

[Redacted]

[Redacted]

[Redacted]

[Redacted]

[Redacted]

[Redacted]

[Redacted]

[Redacted]

[Redacted]

CCI

[Redacted]

[Redacted]

[Redacted]

[Redacted]

CCI [Redacted]

[Redacted]

3.4.1.2 CCI [Redacted]

CCI [Redacted]

[Redacted]

[Redacted]

3.4.1.3 CCI [Redacted]

CCI [Redacted]

[Redacted]

[Redacted]

[Redacted]

CCI

### 3.4.2

CCI

CCI

## 3.5 Other Variables

### 3.5.1 Baseline Characteristics

Baseline characteristics that will be collected or derived are:

- Demographics: age (years), sex, race and ethnicity.
- Patient characteristics: weight, height, body mass index (BMI).
- Medical history: name of past and/or concomitant diseases (verbatim and coded using the latest or current version of the MedDRA dictionary), start and stop dates.
- Nicotine use: smoking status (current, former, never) and pack years.
- Characteristics of NSCLC at diagnosis: original diagnosis date, primary tumour location, histology type, TNM classification, American Joint Committee on Cancer (AJCC) staging.
- Extent of disease at entry of study: current AJCC staging, evidence of disease (yes/no), sites of locally advanced disease, recent progression (yes/no, date).
- Previous disease-related sequential chemoradiotherapy: Total dose, Radiotherapy treated location, Time from completion of radiotherapy to study treatment, Type of previous chemoradiotherapy, best response to previous chemoradiotherapy, Chemotherapy Class,

Chemotherapy regimen used for sequential chemoradiotherapy, Number of chemotherapy cycles.

- Previous treatments for early stage disease (prior to definitive CRT): Radiotherapy treated location, Treatment status, Chemotherapy regimen used for early stage disease prior to CRT.
- Relevant surgical history: surgical procedure (verbatim and coded using the latest or current version of the MedDRA dictionary) and date of surgery.

